ATC	Anatomical Therapeutic Class
ATTR	Amyloid transthyretin
BLQ	Below the lower limit of quantification
BMI	Body mass index
CI	Confidence interval
C _{max}	Maximum plasma concentration at end of infusion
C _{max,ss}	Steady-state C _{max}
C _{min}	Minimum pre-infusion concentration
C _{min,ss}	Steady-state C _{min}
CEC	Clinical Events Committee
CMH	Cochran-Mantel-Haenszel
CMR	Cardiac magnetic resonance
COVID-19	Coronavirus disease 2019
C _{p(30min)}	30-minute post-infusion concentration
C _{p,ss(30min)}	Steady-state C _{p(30min)}
CR	Copy reference
CTCAE	Common Terminology Criteria for Adverse Events
CV	Cardiovascular
DLin-MC3-DMA	1,2-Dilinoleyloxy-N,N-dimethylpropylamine
DMC	Data monitoring committee
ECG	Electrocardiogram

Abbreviation	Definition
eCRF	Electronic case report form
EDC	Electronic data capture
eGFR	Estimated glomerular filtration rate
FAS	Full Analysis Set
FSH	Follicle-stimulating hormone
H/CL	Heart to contralateral lung
hATTR	Hereditary ATTR
HF	Heart failure
HL	Hodges-Lehmann
HLT	High level term
HR	Hazard ratio
IV	Intravenous
ICH	International Council for Harmonisation
IRR	Infusion-related reaction
IRS	Interactive response system
KCCQ	Kansas City Cardiomyopathy Questionnaire
KCCQ-OS	Kansas City Cardiomyopathy Questionnaire-Overall Summary
LLOQ	Lower limit of quantification
LNP	Lipid nanoparticle
log _e	Natural log transformation
LV	Left ventricular
MAR	Missing at random
mBMI	Modified body mass index
MCMC	Markov Chain Monte Carlo
MedDRA	Medical Dictionary for Regulatory Activities
MI	Multiple imputation
MMRM	Mixed effect model repeated measures
MNAR	Missing not at random
Norfolk QoL-DN	Norfolk Quality of Life - Diabetic Neuropathy
NT-proBNP	N-terminal prohormone B-type natriuretic peptide
NYHA	New York Heart Classification
OLE	Open label extension

Abbreviation	Definition
PD	Pharmacodynamic
PEG ₂₀₀₀ -C-DMG	3-N-[(ω-methoxy poly(ethylene glycol)2000) carbamoyl]-1,2-dimyristyloxy-propylamine
PK	Pharmacokinetic
PMM	Pattern mixture model
PND	Polyneuropathy disability
PT	Preferred term
Q1	First quartile
Q3	Third quartile
q3W	Once every 3 weeks
QTc	Corrected QT
QTcF	Fridericia's cube-root corrected QT
SAE	Serious adverse event
SAP	Statistical analysis plan
SD	Standard deviation
SEM	Standard error of the mean
SI	International System of Units
siRNA	Small interfering RNA
SMQ	Standardized MedDRA Query
SOC	System organ class
TTR	Transthyretin
SUSAR	Suspected Unexpected Serious Adverse Reaction
ULN	Upper limit of normal
WHO	World Health Organization
WR	Win ratio
wt	Wild type
wtATTR	Wild type ATTR

1. INTRODUCTION

Transthyretin (TTR)-mediated amyloidosis (ATTR amyloidosis) is a rare, serious, life-threatening, multisystemic disease encompassing hereditary ATTR (hATTR) amyloidosis and wild type ATTR (wtATTR) amyloidosis, which result from either hereditary (genetic mutation) or nonhereditary (ageing) causes, respectively. In ATTR amyloidosis, deposition of TTR in various organs results in progressive, chronically debilitating morbidity and mortality. The most common manifestations of ATTR amyloidosis are polyneuropathy and cardiomyopathy (ie, ATTR amyloidosis with cardiomyopathy).

Patisiran is a small interfering RNA (siRNA) specific for TTR, which is formulated in a hepatotropic lipid nanoparticle (LNP) for intravenous (IV) administration.[Akinc 2010] The patisiran drug product (ALN-TTR02; patisiran-LNP, hereafter referred to as “patisiran”) is designed to significantly suppress liver production of both wild type (wt) and all mutant forms of TTR, thereby having the potential to reduce amyloid formation and provide clinical benefit to patients with ATTR amyloidosis.

The APOLLO-B study (ALN-TTR02-011) is a Phase 3, randomized, double-blind, placebo-controlled, multicenter study designed to evaluate the efficacy and safety of patisiran in adult patients with ATTR amyloidosis with cardiomyopathy.

This statistical analysis plan (SAP) details comprehensive specifications of the efficacy, safety, pharmacodynamic (PD), and pharmacokinetic (PK) data summaries and statistical analyses in support of the clinical study report for Study ALN-TTR02-011. This SAP includes summaries and analyses specified and/or outlined in the protocol Amendment 3, dated 30 June 2021. Additional supportive analyses and changes to planned analyses are also included; notable changes are documented in Section 7. Changes to planned analyses made after database lock will be documented with justification in the clinical study report.

Table, figure, and listing specifications are contained in a separate document.

[figure not shown]
2. STUDY OVERVIEW

2.1. Synopsis of Study Design

The APOLLO-B study is a multicenter, multinational Phase 3 study designed to evaluate the efficacy and safety of patisiran in approximately 300 patients with ATTR amyloidosis (hereditary or wt) with cardiomyopathy; the study is comprised of a 1:1 randomized, double-blind, placebo-controlled period of 12 months followed by an open-label extension (OLE) period of 36 months to evaluate the long-term safety and efficacy of patisiran.

The study design schema is presented in [Figure 1](#).

Figure 1: Study Design

2.2. Randomization Methodology

Using the interactive response system (IRS), patients will be randomized 1:1 to the patisiran or placebo arm. Randomization will be stratified by:

1. Baseline tafamidis (yes vs. no)
2. Type of amyloidosis (hATTR vs. wtATTR amyloidosis with cardiomyopathy)
3. New York Heart Classification (NYHA) Class I or II **and** age < 75 years vs. all other

Patients in the baseline tafamidis use category are defined as patients who are currently on tafamidis (for ≥ 6 months) with disease progression in the opinion of the investigator at baseline.

2.3. Blinding

Treatment assignments will be maintained by the IRS which has controlled access limited to unblinded team members and the unblinded pharmacist/designee preparing the infusion. Any unplanned unblinding occurring during the 12-month double-blind placebo-controlled treatment period (referred to as the 12m-DB period hereafter) will be documented and reported in the clinical study report.

Unblinding is only to occur in the case of patient emergencies or when necessary from a regulatory reporting perspective (eg, Suspected Unexpected Serious Adverse Reaction [SUSAR]), and after all patients have completed the 12m-DB period and the unblinded authorization has been executed. Details about the specifics of the blinding aspects for the study are outlined in the Randomization and Blinding Plan.

2.4. Study Procedures

The schedule of assessments is described in the study protocol (Table 1 and Table 2).

3. OBJECTIVES AND ENDPOINTS

Objectives	Endpoints
Primary	
To evaluate the efficacy of patisiran compared with placebo treatment on functional capacity (6-minute walk test [6-MWT]) in patients with ATTR amyloidosis with cardiomyopathy	Change from baseline at Month 12 in 6-MWT
Secondary	

To evaluate the efficacy of patisiran compared with placebo treatment on:
 
 • Health status and health-related quality of life • Patient mortality, hospitalizations, and urgent heart failure (HF) visits 	
 • Change from baseline at Month 12 in Kansas City Cardiomyopathy Questionnaire Overall Summary (KCCQ-OS) score • Composite endpoint of all-cause mortality, frequency of cardiovascular (CV) events (CV hospitalizations and urgent HF visits) and change from baseline in 6-MWT over the 12-month double-blind period • Composite endpoint of all-cause mortality and frequency of all-cause hospitalizations and urgent HF visits over the 12-month double-blind period
Exploratory	

To evaluate the efficacy of patisiran compared with placebo treatment on:
 
 • All-cause mortality and CV events • Cardiac biomarkers and biomarker-based risk assessment • Manifestations of cardiac amyloid involvement 	
 • Composite endpoint of all-cause mortality and frequency of CV events (CV hospitalizations and urgent HF visits) over the 12-month double-blind period • Change from baseline at Month 12 in: 
 – N-terminal prohormone B-type natriuretic peptide (NT-proBNP) – ATTR amyloidosis disease stage • Change from baseline at Month 12 in: 
 – New York Heart Association (NYHA) Class – Echocardiographic parameters – Modified body mass index (mBMI) – Cardiac magnetic resonance (CMR) parameters – Technetium scintigraphy parameters – Troponin I levels

Objectives	Endpoints
	– Norfolk Quality of Life-Diabetic Neuropathy (Norfolk QoL-DN)
Pharmacodynamics (PD) and Pharmacokinetics (PK)	

 To evaluate the PD effect of patisiran on transthyretin (TTR) reduction To determine the plasma concentration of patisiran and 2 lipid excipients To assess presence of anti-drug antibodies (ADA) 	
 Change from baseline in serum TTR levels through Month 12 Plasma PK exposure parameters (maximum plasma concentration at end of infusion [C_{max}], 30-minute post-infusion concentration [$C_{p(30min)}$], and pre-infusion concentration [C_{min}]) Frequency and titer of ADA
Safety	

 To evaluate the safety and tolerability of patisiran in patients with ATTR amyloidosis with cardiomyopathy 	
 Frequency of adverse events (AEs)

Scoring algorithms for the Kansas City Cardiomyopathy Questionnaire (KCCQ) and Norfolk Quality of Life-Diabetic Neuropathy (Norfolk QoL-DN) questionnaire are included in Appendix 9.3.1 and Appendix 9.3.2, respectively.

4. PATIENT POPULATION

The populations (analysis sets) are defined as follows:

- Full Analysis Set (FAS): All randomized patients who received any amount of study drug. Patients will be analyzed according to the treatment to which they were randomized.
- Safety Analysis Set: All randomized patients who received any amount of study drug. Patients will be summarized according to the treatment actually received.
- PK Analysis Set: All randomized patients who received at least one complete dose of study drug (see Section 6.4) and have at least 1 postdose blood sample for PK parameters and have evaluable PK data.
- PD Analysis Set: All randomized patients who received at least one complete dose of study drug (see Section 6.4) and who have an evaluable baseline and at least one evaluable post-baseline TTR sample.
- All Patisiran Treated Set: All randomized patients who received any amount of patisiran, including patients who took patisiran during the 12m-DB period and patients who first took placebo during the 12m-DB period and switched to patisiran during the OLE period.

The FAS will be used to evaluate efficacy endpoints. Safety during the 12m-DB period will be analyzed using the Safety Analysis Set. The PK and PD Analysis Sets will be used to conduct PK and PD analyses, respectively. The All Patisiran Treated Set will be used to summarize long-

term efficacy and safety data during patisiran treatment (see Section 5.11 for details). The number of patients included in all analysis sets will be provided.

5. GENERAL STATISTICAL METHODS

5.1. Determination of Sample Size

The planned enrollment for this study is 300 patients. For the change from baseline at Month 12 in the 6-MWT, assuming a treatment difference of 33 meters between patisiran and placebo in the treatment-naïve group and 20 meters in patients with baseline tafamidis, the weighted average treatment difference between patisiran and placebo in the overall population is approximately 29 meters (standard deviation [SD] = 75 meters), assuming 70% are in the treatment-naïve group and 30% are in the baseline tafamidis group. A sample size of 300 patients provides >90% power for a 2-sided test to detect a mean difference between treatment arms at a 2-sided alpha = 0.05.

5.2. General Considerations

Categorical variables will be summarized using counts and percentages.

Continuous variables will be summarized using the following descriptive summary statistics: number of patients (n), mean, standard deviation (SD), standard error of the mean (SEM), median, first quartile (Q1), third quartile (Q3), minimum, and maximum. The precision of the measurement for each continuous variable will be used to determine the number of decimal places to present in tables, figures and derived listings. Minimum and maximum values will be reported with the same precision as the units of measure. The mean, SD, SEM, median, Q1 and Q3 will be reported to one greater decimal place. Any values that require transformation to standard units (metric or International System of Units (SI) units) will be converted with the appropriate corresponding precision.

The day of the first dose of study drug administered is defined as Day 1. Study Day is defined as the number of days between the day of the first dose of study drug (Day 1) and the specific time point. The Study Day of a time point of interest is calculated as follows.

If after Day 1, Study Day = date of interest – date of the first dose of study drug + 1

If prior to Day 1, Study Day = date of interest – date of the first dose of study drug

Study days are negative when the time point of interest is prior to Day 1, positive when time of interest is after Day 1. There is no Day 0. For example, the day before the first study drug dose is defined as Day -1.

For the analysis of 6-MWT, only assessments confirmed as valid by the Colorado Prevention Center (6-MWT site training and oversight vendor) will be included. In addition, assessments where the timer was stopped after ≤ 4 minutes will be excluded from analysis.

For safety laboratory parameters, assessments collected and recorded as lower than the lower limit of quantification/detection will be replaced by the lower limit of quantification/detection. Any assessment collected and recorded as greater than the upper limit of quantification will be replaced by the upper limit of quantification.

For all analysis sets except for the All Patisiran Treated Set, summaries will be presented by treatment arm (patisiran and placebo).

For the All Patisiran Treated Set, summaries will be presented by the following groups:

- Patisiran/Patisiran: all patients who received patisiran during the 12m-DB including patients who continued to receive patisiran during the OLE period and patients who discontinued treatment during the 12m-DB period;
- Placebo/Patisiran: all patients who received placebo during the 12m-DB period and switched to patisiran in the OLE period;
- All Patisiran: all patients who received at least one dose of patisiran during either the 12m-DB or OLE periods.

5.3. Computing Environment

All statistical analyses will be conducted using SAS Version 9.4 or newer or R Version 3.4 or newer, unless otherwise noted.

5.4. Baseline Definitions

For 6-MWT, baseline will be defined as the last non-missing value available prior to the first dose of study drug.

For other efficacy parameters, baseline will be defined as the last non-missing value available on or before the date of first dose of study drug, unless otherwise specified.

For TTR, baseline will be defined as the average of all records collected on study, including those from any unscheduled visits, prior to the date and time of first dose.

For each parameter of the 12-lead electrocardiogram (ECG), baseline will be defined as the average of all available readings from the last visit prior to the first dose of study drug.

For all other parameters, baseline will be defined as the last non-missing value available prior to the first dose of study drug, unless otherwise specified.

For the All Patisiran Treated Set, baseline for patients who switched from placebo to patisiran will be redefined as:

- For TTR, the redefined baseline will be calculated as the mean of all TTR assessments performed on or after Month 9 in the 12m-DB period and prior to the first dose in the OLE period.
- For all the other endpoints, the redefined baseline will be defined as the last non-missing value available on or after Month 9 in the 12m-DB period and prior to the first dose in the OLE period, unless otherwise specified. For longitudinal efficacy endpoints, if a patient does not have a Month 12 assessment prior to the first dose in the OLE period, the redefined baseline will be defined as the last non-missing value available on or after Month 9 in the 12m-DB period and up to 3 weeks after the first dose in the OLE period, unless otherwise specified.

5.5. Randomization Stratification Factors

Stratification factors are recorded in both the IRS and the clinical database. In statistical analyses that use randomization stratification factors as covariates, the stratum assignment will reflect the values as recorded in the clinical database. In the presence of stratification errors, the stratification used in analysis may not match that in the IRS.

5.6. Visit Windows

Scheduled visits are expected to follow the protocol schedule. All data will be tabulated and analyzed per the evaluation visit as recorded on the electronic case report form (eCRF) even if the assessment is outside of the visit window.

For 6-MWT and KCCQ, assessments will be conducted at baseline and at Months 6, 9, and 12 in the 12m-DB period and at Months 18, 21, 24, 30, 33, 36, 42 and 48 in the OLE period. For all longitudinal efficacy assessments, if a scheduled post-baseline assessment is not performed, assessments performed within ± 1.5 months of the scheduled assessment will be grouped with the scheduled assessments for that timepoint for analysis, with the following exception:

- For patients randomized to placebo who received patisiran in the OLE period, assessments performed after the first OLE dose will not be grouped with the scheduled Month 12 visits even if they are within ± 1.5 months.

The derived visits will be used for all analyses.

Unless otherwise specified above, data collected at unscheduled visits will be included in by-patient data listings and figures but no assignment to a study visit will be made for the purpose of by-visit summary tabulations. However, unscheduled visits may be used in the calculation of baseline values (as discussed in Section 5.4) and for inclusion in any categorical shift summaries (eg, shift from baseline to “worst” post-baseline value).

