Inability to walk due to progression of ATTR amyloidosis (including patients who are unable to walk due to hospitalization related to progression of ATTR amyloidosis) ^a	Composite variable strategy: For patients who are unable to walk due to progression of ATTR amyloidosis, the missing Month 12 6-MWT change from baseline will be imputed as the worst 10 th percentile change observed across all patients in the 12m-DB period, capped by the worst possible change for the patient (ie, 0 – baseline 6-MWT).
Death (including heart transplant and ventricular assist device placement) not due to COVID-19 ^a	Composite variable strategy: For patients who die (not due to COVID-19), the missing Month 12 6-MWT change from baseline will be imputed as the worst 10 th percentile change observed across all patients in the 12m-DB period, capped by the worst possible change for the patient (ie, 0 – baseline 6-MWT).
Death due to COVID-19	Hypothetical strategy: Missing data due to COVID-19 death will be assumed as MAR.

^a The imputed outcome will be used in the stratified Wilcoxon Rank Sum test and stratified HL estimate but will not be used in the descriptive summaries.

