6.6.1.2. Primary Analysis using the Stratified Wilcoxon Rank Sum Test and Hodges-Lehmann Estimate

The primary analysis will be performed using the stratified Wilcoxon Rank Sum test for the FAS, stratified by baseline tafamidis use (yes vs. no). The analysis will be based on the following assumptions for missing data at Month 12:

1. Patients who die during the 12m-DB period (not due to COVID-19) or who have become unable to walk due to progression of ATTR amyloidosis by Month 12 and have missing data: Assuming that deaths observed in the study will likely be related to worsening of disease, the missing Month 12 6-MWT change from baseline will be imputed as the

worst 10th percentile change, capped by the worst possible change for the patient (ie, 0 – baseline 6-MWT).

2. Patients who have missing data due to other reasons will be imputed assuming data are MAR. Since the pattern of missing data within patients may be non-monotone, multiple imputation will be conducted separately by treatment arm and baseline tafamidis use group using the Markov Chain Monte Carlo (MCMC) method. For each treatment arm/baseline tafamidis use group, the imputation model will include type of amyloidosis (hATTR vs. wtATTR), NYHA class (I/II vs. III), age at randomization (<75 vs. ≥75), baseline NT-proBNP (≤3000 ng/L vs >3000 ng/L), baseline 6-MWT, and all calculated values of change from baseline in 6-MWT at pre-specified visits.

Missing values will be imputed 100 times to generate 100 complete datasets using the procedures described above. The stratified Wilcoxon Rank Sum test will be applied to each imputed dataset for the change from baseline in 6-MWT at Month 12. The Z scores estimated from the stratified Wilcoxon Rank Sum test fit to each imputed dataset will be combined by applying Rubin's rules,[Rubin 1996; Rubin 1987] using SAS PROC MIANALYZE to produce inferential results for the *p* value.

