6.6.1.4. Binary Analyses

Binary analysis for 6-MWT will be conducted on the observed 6-MWT data without imputation. The number and percentage of patients with a ≥ 0 meter increase in 6-MWT from baseline to Month 12 will be calculated for each treatment arm and compared between 2 arms using the Cochran-Mantel-Haenszel (CMH) test, stratified by baseline tafamidis use (yes vs. no). All patients with missing Month 12 data will be counted in the denominator with two exceptions: patients who are missing Month 12 data due to COVID-19 and patients with a 6-MWT assessment collected on or after the onset of a serious COVID-19 AE will be excluded.

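### The ±1.5-month window in SAP 5.6 can put an off-schedule walk into Month 12 for a patient whose Month 12 6-MWT was not done because of death or inability to walk, and that switches off the composite imputation for that patient

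*SAP*

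**What the plan says.** All references are to SAP Amendment 2.1.

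- **Window (5.6).** For longitudinal efficacy measures, "if a scheduled post-baseline assessment is not performed, assessments performed within ± 1.5 months of the scheduled assessment will be grouped" with that visit. The section adds: "The derived visits will be used for all analyses". For 6-MWT, "assessments will be conducted at baseline and at Months 6, 9, and 12 in the 12m-DB period".
- **Only exception (5.6).** For placebo patients who went on to OLE patisiran, "assessments performed after the first OLE dose will not be grouped with the scheduled Month 12 visits". Death and inability to walk are not mentioned.
- **Death (Table 1).** The strategy is composite: "For patients who die (not due to COVID-19), the missing Month 12 6-MWT change from baseline will be imputed" with the worst 10th percentile change, capped at loss of the whole baseline distance. Heart transplant and ventricular assist device placement count as death.
- **Inability to walk (Table 1, 6.6.1.2).** The same value is imputed, and 6.6.1.2 applies it to patients "who have become unable to walk due to progression of ATTR amyloidosis by Month 12 and have missing data". Table 1 includes patients who cannot walk because they are in hospital for progression.
- **Same condition elsewhere.** Section 5.8.2, Sensitivity Analyses 1 and 2 (6.6.1.3) and Appendix 9.1 also act only on a missing Month 12 value.
- **Binary analysis (6.6.1.4).** Observed data are used without imputation. "All patients with missing Month 12 data will be counted in the denominator with two exceptions", both related to COVID-19.

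**The concern.** The window decides whether Month 12 is missing. The composite strategy acts only on what is missing, and no sentence says that death or inability takes precedence over the window. A walk from before the failure, or from after recovery, can therefore replace the failure value that the estimand assigns. Which patients escape depends on the chance that an extra walk was recorded, not on their clinical outcome.

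This concerns the primary endpoint, which gates four further tests in the hierarchy of 5.7. The arms are also not treated alike. Sections 5.6 and 5.11 let a walk after the first OLE dose count as Month 12 for a patisiran patient, but the exception in 5.6 bars it for a placebo patient who started OLE patisiran.

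**Working it through.** **1. The plan's own figure.** Inputs from 5.1 and 2.2: 33 m and 20 m weighted 70/30, SD 75 m, N = 300 allocated 1:1, two-sided alpha 0.05.
- Weighted difference: 0.7 × 33 + 0.3 × 20 = 29.1 m, stated as about 29 m.
- Standard error: 75 × √(2/150) = 8.66 m. Power is about Φ(29/8.66 − 1.96) = Φ(1.39), or 91.8%.
- 90% power needs 141 per arm. The stated >90% reproduces; the point does not rest on it.

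**2. Reach of the window.** 12 ± 1.5 gives Months 10.5 to 13.5, or about Days 320 to 411 at 30.4375 days per month. A nominal Month 9 walk lies 3 months before Month 12, twice the allowed distance, so it cannot fill Month 12.

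**3. The rules applied to hypothetical records.**

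| Record | Derived Month 12 | Result |
|---|---|---|
| Unscheduled walk at Month 10.8, −20 m; cardiac death at Month 11.5 | −20 m | Not missing, death not imputed |
| The same, but walk +5 m | +5 m | Not imputed; a responder in the binary analysis |
| Patisiran; in hospital for progression at Month 12; OLE dose; walk at Month 13 | Month 13 walk | Not imputed |
| Placebo, same course | None (exception in 5.6) | Worst 10th percentile imputed |
| Death at Month 11.5, last walk on schedule at Month 9 | None | Imputed as intended |

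**4. How many can be affected.** The SAP gives no event rates or timing, so these are assumptions. The share of deaths or permanent losses of walking in Months 10.5 to 12 is:
- even timing: 1 − 10.5/12 = 12.5%;
- density rising linearly: 1 − (10.5/12)² = 23.4%;
- density rising quadratically: 1 − (10.5/12)³ = 33.0%.

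With event rates of 3-15% of 300 (9 to 45 patients) and even timing, at most 9 × 0.125 = 1.1 to 45 × 0.125 = 5.6 patients are affected if every one has a windowed walk. If 10% do, it is 0.1 to 0.6. Under quadratic timing the maximum is 3.0 to 14.9. Temporary inability and transplant or device patients are outside this bound, because they may walk later in the window.

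**5. Effect per replaced patient.** A stratified Wilcoxon simulation (1,500 runs per scenario) used 150 per arm, SD 75 m, effects of 33/20 m and 25% on tafamidis. It assumed 6 patisiran and 9 placebo composite events and a windowed walk of mean −50 m (SD 50). The composite value was about −127 m.
- One patisiran failure replaced: +0.52 m, Z +0.064.
- One placebo failure replaced: −0.55 m, Z −0.053.
- Rough check on the mean scale: (127 − 50)/150 = 0.51 m.
- At 12.5%, at most 6 × 0.125 = 0.75 patisiran and 9 × 0.125 = 1.1 placebo failures are replaced. The net shift is 0.75 × 0.52 − 1.125 × 0.55 = −0.23 m.

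**6. Power, as illustration.** An unstratified Wilcoxon simulation (3,000 runs) assumed 5% patisiran and 10% placebo events. Power was 95.0% with no replacement, 93.7% with 12.5% replaced and 92.9% with 33%. Simulation error is about 0.4 to 0.5 points per figure. Replaced patients kept an ordinary value for their arm, which is probably better than a walk close to failure, so the loss is probably overstated.

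**7. Binary analysis.** For a walk distributed N(−50, 50), the chance of a change ≥ 0 is 1 − Φ(1) = 16%. It is 9% for N(−80, 60) and 31% for N(−25, 50).

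**The case against.** The best defence is that the plan can be executed as written: derive visits first, then impute whatever is still missing. The condition that Month 12 be missing also has a proper purpose, since it keeps a genuine Month 12 walk in someone who dies later. Both points are fair. Neither explains why an off-schedule walk should stand in for a visit that could not take place because of the event Table 1 treats as failure.

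The limits on reach stand in full:
- A reader might infer that the composite imputation never applies to deaths or losses of walking. The visit schedule rules that out: without an off-schedule walk in the window the value stays missing and is imputed.
- A Month 9 walk done late, say at Month 10.6, looks like another route. Section 5.6 first says that data are analysed under the visit recorded on the eCRF, so such a walk should stay at Month 9.
- The current 5.6 does not say which visits generate off-schedule walks. Superseded SAP versions mention unscheduled and early-discontinuation visits, but the frequency is unknown.
- The win ratio is largely protected. Deaths are settled at Step 1, and Step 3 has its own rule for a patient unable to walk.
- The binary analysis is supportive and uses observed data, so a misclassified responder there does not breach the primary estimand.

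**Conclusion.** The collision is in the current text: a stated derivation rule overrides a stated estimand strategy for some patients. It affects the primary analysis, Sensitivity Analyses 1 and 2 and Appendix 9.1, and it can make a patient who died before Month 12 a responder in the binary analysis. It reaches only patients with a recorded off-schedule walk in the window. Under the timing assumptions above, 67-87.5% or more of deaths and permanent losses of walking are still imputed as intended.

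The effect is small, about 0.5 m per replaced patient against a planned 29 m. A reader might infer a general bias towards patisiran; the documents do not support that. The sign depends on the arm, and with more failures on placebo, as assumed above, the rule works slightly against patisiran. Only the handling of walks after the first OLE dose favours patisiran by construction. Nor does the timing share support sizing the problem by several replacements in one arm: even timing gives at most about one per arm for 6 and 9 events. The reason to act is agreement between estimand and derivation, at very low cost.

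**What to change.** Add a second exception to 5.6. For 6-MWT, nothing is grouped with a Month 12 visit that was not performed because the patient had died of a cause other than COVID-19 (heart transplant and ventricular assist device placement counting as death, as in Table 1) or could not walk because of ATTR progression. Month 12 then counts as missing and Table 1 applies, in the primary analysis and in Sensitivity Analyses 1 and 2, with a cross-reference in Appendix 9.1. State in 6.6.1.4 that these patients are non-responders. A walk actually performed at the Month 12 visit is unaffected.

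This also removes the difference between arms for temporary inability, because a later walk would no longer fill Month 12 in either arm. The cost is a sentence in 5.6, short conforming text and one programming condition. The downside is that a few observed off-schedule walks are not used at Month 12; they remain in the listings.
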